16.33 Exploratory & Correlative Endpoints (Both Cohorts)

16.331 Patient-reported outcomes: Patient-reported outcomes will be an exploratory component of this trial. Patient-reported symptoms and quality of life (QOL) will be described at each time point using the mean, confidence interval, median, and range. The MPN-SAF will be analyzed using published scoring algorithms. For the MPN-SAF, we will investigate changes in individual symptoms, changes in a symptom scale composed of symptoms specific to MF patients (night sweats, itching, abdominal discomfort, abdominal pain, early satiety, and bone pain) similar to the subset of symptoms used in the COMFORT clinical trials, and changes in the MPN Total Symptom Score (MPN-TSS, Emanuel et al, J Clin Oncol 2012 [in press]). Interpretation will take into consideration that the MPN-TSS includes symptoms potentially irrelevant to this MF population. Graphical procedures will include stream plots of individual patient scores and plots of average values over time. Correlational analyses will be done to determine the relationships among patients-reported symptoms and QOL, as well as with clinical outcomes (best overall response and overall survival) and clinician-assessed symptoms (NCI CTCAE v4). Such correlations will be done at single data time points.

16.4 Data & Safety Monitoring:

16.41 The study chair(s) and the study statistician will review the study at least twice a year to identify accrual, adverse event, and any endpoint problems that might be developing. The Mayo Clinic Cancer Center (MCCC) Data Safety Monitoring Board (DSMB) is responsible for reviewing accrual and safety data for this trial at least twice a year, based on reports provided by the MCCC Statistical Office.

16.42 Adverse Event Stopping Rules: The stopping rules specified below are based on the knowledge available at study development. The stopping rule applies to the

overall study, regardless of cohort. We note that the Adverse Event Stopping Rule may be adjusted in the event of either (1) the study re-opening to accrual or (2) at any time during the conduct of the trial and in consideration of newly acquired information regarding the adverse event profile of the treatment(s) under investigation. The study team may choose to suspend accrual because of unexpected adverse event profiles that have not crossed the specified rule below.

Accrual will be temporarily suspended to this study if at any time we observe events considered at least possibly related to study treatment (i.e. an adverse event with attribute specified as “possible”, “probable”, or “definite”) that satisfy the following:

- if 2 or more patients in the first 6 treated patients in either cohort (or 30% after the first 6 treated patients have been accrued) experience a grade 4 or higher non-hematologic adverse event.

We note that we will review grade 4 and 5 adverse events deemed “unrelated” or “unlikely to be related”, to verify their attribution and to monitor the emergence of a previously unrecognized treatment-related adverse event.

16.5 Results Reporting on ClinicalTrials.gov: At study activation, this study will have been registered within the “ClinicalTrials.gov” website. The Primary and Secondary Endpoints (i.e., “Outcome Measures”) along with other required information for this study will be reported on ClinicalTrials.gov. For purposes of timing of the Results Reporting, the initial estimated completion date for the Primary Endpoint of this study is 19 months after the study opens to accrual. The definition of “Primary Endpoint Completion Date” (PECD) for this study is at the time the last patient registered has completed treatment.

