16.32 Definitions and Analyses of Secondary Endpoints (Both Cohorts)

16.321 Survival time is defined as the time from registration to death due to any cause. The distribution of survival time will be estimated using the method of Kaplan-Meier (1958).

16.322 Adverse events: All eligible patients that have initiated treatment will be considered evaluable for assessing adverse event rate(s). The maximum grade for each type of adverse event will be recorded for each patient, and frequency tables will be reviewed to determine patterns. Additionally, the relationship of the adverse event(s) to the study treatment will be taken into consideration.

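### Section 16.331 relates symptom scores to overall survival without a censoring-aware method, and its visit means rest on whoever still returns a questionnaire

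*Combined protocol and SAP*

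**What the plan says.** **Survival.** Section 16.331 proposes correlational analyses among the patient-reported measures, "as well as with clinical outcomes (best overall response and overall survival" and with clinician-graded symptoms. It adds: "Such correlations will be done at single data time points". It names no coefficient or model and gives no rule for patients alive at the analysis. For the survival endpoint itself, section 16.321 counts time from registration to death from any cause and states: "The distribution of survival time will be estimated using the method of Kaplan-Meier (1958". Section 18.1 ends follow-up 3 years after registration.

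**Trends.** Section 16.331 also states: "Patient-reported symptoms and quality of life (QOL) will be described at each time point using the mean, confidence interval, median, and range". The graphs are to include "stream plots of individual patient scores" and "plots of average values over time". Changes are covered too: "we will investigate changes in individual symptoms", along with changes in a myelofibrosis symptom subset and in the total score. The plan gives no rule for missing questionnaires and does not ask for the number contributing at each visit.

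**Collection.** Section 4.0 schedules the questionnaire at baseline, before cycles 2, 3, 6, 9 and 12, every third cycle after that, and at treatment discontinuation. Under section 13.0, patients who progress or stop treatment move to event monitoring, for which section 18.1 lists no questionnaire.

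**The concern.** A patient alive at the analysis has no known survival time, only a lower bound. A plain correlation must either treat that bound as the survival time or drop the patient, and either choice loses information about the ordering of survival. Kaplan-Meier in section 16.321 deals with censoring for the survival curve, but nothing carries a comparable method into section 16.331.

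The second issue is who is averaged. Later visits include only patients still on treatment, apart from one questionnaire at discontinuation. If patients with worse scores leave sooner, the average curve falls even though nobody feels better. The protocol makes this plausible: several total-score items (fatigue, concentration, itching, fever) also appear among the interferon effects in section 15.17, and section 8.0 lets toxicity lead to dose reduction and finally discontinuation.

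At stake is the reading of exploratory objective 2.31. A real link between symptoms and survival could be missed, and a falling symptom curve could be taken for benefit.

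**Working it through.** **1. Follow-up (16.22, 16.23, 18.1).** There are at most 19 patients, accruing at about 1 per month, with 6 months' follow-up for the last. Analysis time = 19/1 + 6 = 25 months, which reproduces the plan's figure. A patient entering at month *e* has 25 − *e* months, so with *e* from 0 to about 19 the range is about 25 down to 6 months. The cap is 36 months.

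**2. Effect on a correlation with recorded time.** The documents give no median survival and no strength of association, so both are assumed. The model is: score standard normal; survival exponential with hazard (ln 2 / median) × exp(b × score); recorded time = min(survival, follow-up); 19 patients; Spearman correlation of score with true and with recorded time, averaged over simulated trials.

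| Assumption | Follow-up | Censored | True | With recorded time |
|---|---|---|---|---|
| b = 0.5, median 18–72 months | month 25 | 56–86% | about -0.37 | -0.24 to -0.09 |
| b = 0.7, median 24–120 months | month 25 | 61–89% | about -0.47 | -0.28 to -0.08 |
| b = 0.7, median 24–120 months | 36 months each | 36–78% | about -0.47 | -0.44 to -0.29 |

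The first row spans separate simulation runs of the same set-up. Using deaths only is worse: with b = 0.7 and 36 months each, the value is -0.21 to -0.07.

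**3. No association.** With b = 0, month 25 and medians of 18, 36 and 72 months, the correlation averages 0.00 and is significant at 5% in 5.0–5.3% of trials. Its standard deviation is about 0.23.

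**4. What a censoring-aware method gains.** With b = 0.5 at month 25, the share of trials significant at 5% is:

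| Assumed median survival | Correlation with recorded time | Cohort-stratified Cox score test |
|---|---|---|
| 18 months | 19% | 25% |
| 36 months | 10% | 15% |
| 72 months | 7% | 10% |

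The gain is consistent, but power stays low. Expected deaths are 19 × (1 − 0.86) ≈ 3 to 19 × (1 − 0.56) ≈ 8. Fewer than 5 deaths occur in 41% of trials at a median of 36 months and in 87% at 72 months.

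**5. Effect of dropout on the visit mean.** The documents give no score mean, standard deviation or dropout rate, so these are assumed. In both examples no patient's underlying score changes.

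- *First example:* 13 patients, mean 30, SD 12, about half leaving by Cycle 6, worse scores leaving more often. The baseline mean is 30.1 and the Cycle 6 mean of those remaining is 23.8. Their mean change from own baseline is -0.06.
- *Second example:* 19 patients, mean 30, between-patient SD 15, within-patient SD 8. The chance of leaving in each visit interval is 5%, 10% or 20% at a score of 30. The log-odds of leaving rise by 0, 0.5 or 1 per 15 points. Mean of those remaining at the fifth on-treatment visit:

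| Chance of leaving per interval | Unrelated to score | 0.5 per 15 points | 1 per 15 points |
|---|---|---|---|
| 5% | 30.1 | 28.5 | 26.3 |
| 10% | 30.1 | 27.0 | 24.2 |
| 20% | 30.0 | 24.6 | 21.1 |

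The spurious fall is about 1.6 to 9 points when leaving depends on the score and about 0 when it does not. Change from own baseline among those remaining is about 0 in every cell.

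**The case against.** The strongest replies, and what stands of each:

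- **The plan does not say that survival is treated as fully observed.** Correct. A reader might infer it from the word correlation, but no coefficient is named and section 16.321 recognises censoring. The defect is that the method is left open.
- **The survival error is not false prognosis.** Correct. Because recorded time follows enrolment date, a reader might infer that the correlation would mainly reflect enrolment, or would make the score look prognostic. Step 3 shows otherwise: with scores unrelated to entry date, the error rate stays at about 5%. What is lost is signal.
- **Counting survival from registration does not inflate the correlation for later scores.** Correct in substance. At one scheduled visit all contributors have survived nearly the same time, and subtracting a constant leaves the correlation unchanged. Small differences in visit timing are immaterial.
- **Month 25 is the harshest case.** Partly. Section 16.3 ties analysis timing to data maturity, and nothing fixes this correlation at month 25. At 3 years the loss is little to moderate, though still visible when survival is long.
- **Change analyses, individual plots and a discontinuation questionnaire are already planned.** Correct, and they make dropout partly visible. But change is not defined, contributing numbers are not required, and one discontinuation form does not replace later visits.
- **A Cox model with so few deaths may be close to inestimable.** A fair limit. It calls for reporting the number of deaths and for a stated fallback, and it applies equally to the correlation.

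**Conclusion.** The point holds in limited form. Section 16.331 leaves open how censored survival enters the correlations. An ordinary correlation would be valid under no association, but at month 25 it would shrink a real one of about -0.37 to between -0.24 and -0.09. At 3 years the loss is little to moderate. The raw visit means can fall from 30 to about 24 with no true change if about half the patients leave and leaving depends on the score.

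All these sizes rest on assumed survival, effect, score and dropout figures. A reader might infer that censoring and dropout are bound to determine both results. The documents do not support that, because they give none of those figures and the dropout shift is about 0 when leaving is unrelated to score. The analysis is exploratory, includes at most 19 patients and feeds no decision rule. It is worth correcting because the better method is cheap, but the trial's main conclusion does not depend on it.

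**What to change.** 1. **Survival.** Replace the correlation by a Cox model (or a censoring-aware concordance measure) of survival on the baseline score and, as a landmark analysis, on the Cycle 3 Day 1 score with time counted from that visit. Stratify by cohort, since constitutional symptoms are one of the DIPSS factors that define the cohorts (Appendix VI). Report the estimate, its interval and the number of deaths, and state that it is not estimable if deaths are too few.
2. **Trends.** Make change from each patient's own baseline the main summary, from a repeated-measures mixed model on all observed visits, by cohort where numbers allow. Show the number contributing at each visit and keep the individual plots. Visit means can stay as description.
3. **Reconcile.** Section 4.0 schedules a questionnaire at discontinuation, but the section 18.1 form table, as it reads here, marks none at end of treatment. Sections 16.23 and 16.3 give 25 and 19 months for the same 6-month follow-up of the last patient.

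The cost is SAP wording and a few lines of code, with no new data. The downsides are wide intervals from few deaths and the mixed model's assumption that questionnaires are missing at random.

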6.2 Correlative Research

A mandatory correlative research component is part of this study, the patient will be automatically registered onto this component (see Sections 3.19c and 14.0).

6.3 Documentation of IRB approval must be on file in the Registration Office before an investigator may register any patients.

In addition to submitting initial IRB approval documents, ongoing IRB approval documentation must be on file (no less than annually) at the Registration Office [REDACTED] [REDACTED] If the necessary documentation is not submitted in advance of attempting patient registration, the registration will not be accepted and the patient may not be enrolled in the protocol until the situation is resolved.

When the study has been permanently closed to patient enrollment, submission of annual IRB approvals to the Registration Office is no longer necessary.

6.4 Prior to accepting the registration, registration application will verify the following:

- IRB approval at the registering institution
- Patient eligibility
- Existence of a signed consent form

- Existence of a signed authorization for use and disclosure of protected health information

6.5 At the time of registration, the following will be recorded:

- Patient has/not given permission to store and use his/her sample(s) for future research of Myelofibrosis at Mayo.
- Patient has/not given permission to store and use his/her sample(s) for future research to learn, prevent, or treat other health problems.
- Patient has/not given permission for MCCC to give his/her sample(s) to researchers at other institutions.

6.6 Treatment cannot begin prior to registration and must begin \leq 14 days after registration.

6.7 Pretreatment tests/procedures (see Section 4.0) must be completed within the guidelines specified on the test schedule.

6.8 All required baseline symptoms (see Section 10.51) must be documented and graded.

6.9 Treatment on this protocol must commence at Mayo Clinic Arizona under the supervision of a hematologist or healthcare professional.

6.9a Study drug is available on site.

6.9b Patient questionnaire booklet is available on site; copies are not acceptable for this submission.

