10.5 Other Required Reporting

10.51 Adverse events to be graded at each evaluation and pretreatment symptoms/conditions to be evaluated at baseline per the CTCAE v4.0 grading unless otherwise stated in the table below:

System/Organ/Class (SOC)	Adverse event/Symptoms	Baseline	Each evaluation
Investigations	White blood cell decreased	X	X
	Neutrophil count decreased	X	X
	Platelet count decreased	X	X
Gastrointestinal Disorders	Diarrhea		X
	# of stools	X	
	Nausea	X	X
	Vomiting	X	X

10.52 Submit via appropriate MCCC Case Report Forms (i.e., paper or electronic, as applicable) the following AEs experienced by a patient and not specified in Section 10.51

10.521 Grade 2 AEs deemed *possibly, probably, or definitely* related to the study treatment or procedure.

10.522 Grade 3 and 4 AEs regardless of attribution to the study treatment or procedure.

10.523 Grade 5 AEs (Deaths)

10.5231 Any death within 30 days of the patient's last study treatment or procedure regardless of attribution to the study treatment or procedure.

10.5232 Any death more than 30 days after the patient's last study treatment or procedure that is felt to be at least possibly treatment related must also be submitted as a Grade 5 AE, with a CTCAE type and attribution assigned.

10.53 Refer to the instructions in the Forms Packet (or electronic data entry screens, as applicable) regarding the submission of late occurring AEs following completion of the Active Monitoring Phase (i.e., compliance with Test Schedule in Section 4.0).

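### Section 16.331 plans to correlate MPN-SAF symptoms with clinician CTCAE grades, but Sections 10.51 and 10.52 require only severe or drug-attributed grades for those symptoms

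*Combined protocol and SAP*

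**What the plan says.** Section 16.331 treats patient-reported outcomes as exploratory. It plans to relate patient-reported symptoms and quality of life to clinical outcomes and to "clinician-assessed symptoms (NCI CTCAE v4" grades. On timing it says: "Such correlations will be done at single data time points".

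The clinician grades would come from Section 10.5. Section 10.51 lists "Adverse events to be graded at each evaluation and pretreatment symptoms/conditions to be evaluated at baseline per the CTCAE v4.0 grading". The list holds three blood counts plus diarrhea, nausea and vomiting; for diarrhea, the baseline entry is a stool count. Section 6.8 points to the same list for baseline: "All required baseline symptoms (see Section 10.51) must be documented and graded".

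All other events fall under Section 10.52, which covers "the following AEs experienced by a patient and not specified in Section 10.51". It asks for three groups:
- "Grade 2 AEs deemed *possibly, probably, or definitely* related to the study treatment or procedure" (10.521)
- "Grade 3 and 4 AEs regardless of attribution to the study treatment or procedure" (10.522)
- deaths (10.523)

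**The concern.** A correlation at one time point needs a clinician grade for the symptom, for each patient, at that time. For the symptoms the MPN-SAF measures, the plan does not require one. It requires a record only when the symptom is severe, or is moderate and thought to be at least possibly caused by P1101.

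The filter works on one side of the comparison only. The MPN-SAF scores a symptom whatever its cause, and Section 1.1 calls constitutional symptoms hallmarks of the disease. Moderate symptoms that the clinician puts down to myelofibrosis are the grade 2 events left out. Agreement between patient and clinician could then look lower than it is, and ungraded symptoms cannot be reliably reconstructed after the visit.

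**Working it through.** **1. Overlap of the lists.** The documents give no figure for this analysis, so there is none to reproduce. The check is a comparison of lists.

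| Source | Symptoms | Shared with the 10.51 symptoms (diarrhea, nausea, vomiting) |
|---|---|---|
| 16.331, MF-specific scale | "night sweats, itching, abdominal discomfort, abdominal pain, early satiety, and bone pain" | 0 of 6 |
| Section 11, MPN-SAF TSS | ten items, including fatigue, night sweats, itching, bone pain, fever and weight loss | 0 of 10 |
| Appendix IV, full MPN-SAF | the above plus headache, dizziness, numbness, sleep, mood, sexual function, cough and others | 0 |

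**2. What a blank means for an MPN-SAF symptom.**

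| True state | Required on the form? |
|---|---|
| Grade 0 | no |
| Grade 1, non-serious | no |
| Grade 2, unrelated or unlikely, non-serious | no |
| Grade 2, possible, probable or definite | yes (10.521) |
| Grade 3 or 4 | yes (10.522) |

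The first three rows cannot be told apart in the required data.

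**3. Illustrative size.** Every input here is an assumption; none comes from the documents. Let the patient score and the clinician's latent severity be bivariate normal with correlation ρ, and cut severity at 0, 0.8, 1.6 and 2.4:
- grade 0: Φ(0) = 50%
- grade 1: Φ(0.8) − Φ(0) = 28.8%
- grade 2: Φ(1.6) − Φ(0.8) = 15.7%
- grade 3: Φ(2.4) − Φ(1.6) = 4.7%
- grade 4: 1 − Φ(2.4) = 0.8%

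The recorded grade equals the true grade if it is 3 or 4, or if it is 2 and attributed to drug; otherwise it is read as 0. With ρ = 0.7 the Spearman correlation under full grading is 0.62. After the filter (accurate to about 0.01):

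| Share of grade 2 attributed | Correlation seen |
|---|---|
| 25% | 0.36 |
| 50% | 0.40 |
| 75% | 0.45 |
| 90% | 0.48 |

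With half attributed, other full-grading values fall as follows: 0.17 to 0.12, 0.44 to 0.29, and 0.82 to 0.51.

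Patients with a non-zero recorded grade, half attributed: 4.7 + 0.8 + 0.5 × 15.7 = 13.4%, against 50% under full grading. Of 19 patients (Section 16.22) that is 0.134 × 19 ≈ 2.5, against 9.5.

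**4. Sensitivity.** A second model rounds the patient score to 0–10, uses grade 0/1/2/3 shares of 30/40/25/5%, 50/30/15/5% or 15/40/35/10%, and attributes 20% to 80% of grade 2 events.

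| Latent ρ | Full grading | After the filter |
|---|---|---|
| 0.5 | 0.43–0.45 | 0.24–0.38 |
| 0.7 | 0.62–0.64 | 0.33–0.54 |

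The relative loss runs from about (0.64 − 0.54)/0.64 = 16% to (0.62 − 0.33)/0.62 = 47%. About 1.5 to 7 of 19 patients have a non-zero recorded grade for a symptom, against 9.5 to 16.

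**The case against.** **Lower grades may still be captured.** Section 10.52 is a submission rule. A serious event of lower grade goes to the sponsor whatever its attribution (10.4) and then enters routine data (10.11). Section 4.0 schedules adverse event monitoring throughout, Section 18 lists baseline and on-treatment adverse event forms whose fields are not shown, and Section 16.322 records the maximum grade of each event type with no stated floor. A reader might infer that lower grades never reach the database; the documents do not support that. They do show that such grades are not required. A maximum grade per patient is also not a grade at a time point.

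**Part of the analysis can be done as planned.** Section 16.331 does not demand item-to-item matching. Nausea and vomiting are graded at baseline and each evaluation, and the questionnaire is also completed before registration. These grades can be correlated with quality of life or MPN-SAF totals without any attribution filter. A reader might infer that nothing can be computed at baseline; that is true only of matched symptoms.

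**Many symptoms could pass the filter.** Section 15.17 lists fatigue, fever, headache, pruritus, sweating, cough and others as effects of P1101 or its class, and a judgement of possible is enough. This stands, and is why the range extends to 90% attributed. Grade 1 is still lost.

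**Sampling error is as large as the bias.** With 19 patients in the first model (ρ = 0.7, half attributed), 95% of sample correlations fall between roughly 0.25 and 0.85 under full grading, and between about −0.01 and 0.69 after the filter. This also stands: full grading would remove the bias but leave an imprecise estimate.

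**Conclusion.** The mismatch is confirmed by the text. For MPN-SAF symptoms, the required CTCAE data leave out non-serious grade 1 and non-serious unrelated grade 2 events, and contain no baseline grade. If blanks are read as grade 0, for which Section 16.331 gives no rule either way, matched-symptom correlations are biased toward zero. The illustrative size is 0.62 seen as about 0.36 to 0.48. It rests on an assumed grade mix, latent correlation and attributed share (25% to 90%).

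Two stronger readings are not supported. A reader might infer that the correlation will look weak whatever the true agreement, but in the model it still rises with the true value (0.17, 0.44, 0.62 and 0.82 appear as 0.12, 0.29, 0.40 and 0.51). A reader might also infer that the trial will report that patients and clinicians disagree, but the plan sets no threshold and commits to no such claim.

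Severity is minor. The analysis is exploratory, in at most 19 patients. Best overall response, the two-stage decision rule, the adverse event stopping rule, and the MPN-SAF total score used in the response criteria are unaffected.

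**What to change.** Choose one of two changes.

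1. Add to Section 10.51 a short list of CTCAE v4 terms that match the MF-specific and TSS symptoms used in Section 16.331: for example fatigue, pruritus, night sweats, bone pain, fever, abdominal pain, early satiety and weight loss, with the closest term named where there is no exact counterpart. Have them graded at baseline and each evaluation, at all grades including 0 and regardless of attribution. Section 6.8 then carries the baseline requirement without further change. The list need not cover all of Appendix IV.
2. Delete the matched-symptom CTCAE correlation from Section 16.331 and limit the clinician side to the symptoms graded under Section 10.51.

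The first costs a few more form items at visits where adverse events are already assessed and the questionnaire is already completed, for at most 19 patients. It has to be in place while patients are on study. The second costs one exploratory analysis.
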